## **ABSTRACT**

**Background:** Ultra-wide-diameter implants (7 mm to 9 mm diameter) are gaining favor for immediate placement in the posterior area because they allow for increased engagement of molar socket walls, reduce the need to bone graft and provide better stress distribution under the high occlusal loads in the posterior area.

**Aim of this study:** To evaluate both the clinical and radiographical outcome on osseointegration and peri-implant bone density when using ultra wide diameter implant placed immediately in molar extraction socket.

**Plan of the study:** 12 implants for 12 patients will be immediately placed in fresh extracted molar sockets without flap or bone grafts. After six months, cement retained crown will be loaded to the implant. Clinical and radiographic parameters will be evaluated.

**Results:** Will be statistically analyzed using the Statistical Package for Social Science (SPSS) software version 20.0.

**Keywords:** dental implant, immediate placement, ultra-wide.

## INTRODUCTION

Alveolar bone undergoes dimensional changes vertically and horizontally after tooth extraction as a result of periodontal loss and bundle bone resorption in the tooth socket leading to reduction of bone volume that affects negatively the dental implant placement and the restorative treatment functionally and esthetically.

The first year following tooth loss in premolar and molar area, up to 50% ridge width reduction occurs, where two-thirds of the total reduction occur within the first three months' post extraction.

To overcome these unfavorable changes, immediate implant placement is recommended at the time of tooth removal for less buccolingual bone reduction and wider crest compared to the delayed implant placement.

However, Immediate implant placement in molar extraction socket is more critical unlike in single root sockets, this is due to many factors such as complex anatomy of molar roots with larger socket dimensions and also the high mechanical forces exerted on molar sites.

Immediate implant as a single surgical procedure has many advantages. These advantages include ideal implant positioning, preservation of socket bone and shortened treatment time. Furthermore, studies reported less amount of bone loss when the implant is placed immediately after tooth extraction.

The final outcome of immediate placement depends on many important factors. These factors include the preservation of the walls of alveolar bone during extraction especially the buccal plate, the oral health and hygiene

conditions, the surgical and prosthetic protocol followed, the surgical technique used, the implant position in the socket, the use of bone grafts and the elevation approach either flapless or with a flap.

Successful immediate implant placement is determined by primary stability which is an essential factor which is also very challenging in molar sockets due to many reasons such as the presence of multiple roots with large socket voids, and the anatomical limitations due to presence of maxillary sinus and inferior alveolar nerve.

Implant design including “pitch, width, depth, shape of the thread, and crestal module” is an important factor in determining the stress distribution and primary stability during osseointegration in immediate loading implants.

Using conventional implant in one of the molar root sockets leads to many prosthetic and maintenance complications, it compromises the emergence profile which could be avoided by placing the implant into the interradicular septum for more prosthetic improvement and long term maintenance, However, engaging to the socket septum can lead to inaccurate implant site preparation and requires additional bone augmentation to fill the residual socket spaces.

Wider diameter implants in immediate molar implant placement have many advantages over the narrow conventional implant. These advantages are increasing the contact area engaged the implant with the socket walls and interradicular area for better osseointegration and more favorable occlusal forces distribution it also enhances the emergence profile and permits using wider and stronger prosthetic components.

Ultra wide dental implants increase primary stability, permit greater bone contact and reduce the residual space in molar socket so reduce the need to bone graft with a predictable outcome and very little bone loss.

This technique requires high clinical experience in teeth removal atraumatically for bone preservation and site preparation, and also requires a careful case selection for a successful treatment.

Hattingh et al., concluded that the immediate placement of ultrawide diameter dental implant in fresh extracted molar socket following atraumatic extraction without any flaps has a predictable outcome esthetically with minimal contour changes and accepted stability over time.

The null hypothesis is that using the ultra-wide implant placed immediately after molar extraction has no significant effect on implant stability and peri-implant bone density.

## **AIM OF THE STUDY**

The aim of the study is to evaluate both the clinical and radiographical outcome on osteointegration and peri-implant bone density when using ultra wide diameter implant placed immediately in molar extraction socket.

# PLAN OF THE STUDY

## Study Design

The study is a single arm clinical trial. It will be set up and reported according to the CONSORT guidelines.

The PICO question: Does the immediate placement of ultra wide diameter implant in non-restorable mandibular molar socket will enhance primary stability and peri-implant bone density?

Type of patients or population: patients with age range 20-40 years old having non-restorable mandibular molar teeth.

Type of Intervention: immediate placement of ultra wide diameter implant.

Outcomes: wound healing, socket dimensions, crestal bone loss, implant stability and bone density will be the main outcome measures of this study.

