## Summary Statement

Sample size was estimated assuming 5% alpha error and 80% study power. Tsallarico et al reported that the mean Implant Stability Quotient (ISQ) values at baseline for ultra-wide implants was  $65.5 \pm 7.6$  and  $78.8 \pm 2.8$  after 6 months of implant placement. The sample will be stratified by gender into two groups. Sample size was calculated to be 5 patients per group, increased to 6 patients to make up for loss to follow up. Total sample size = number per group  $\times$  number of groups =  $6 \times 2 = 12$  patients.

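### With one arm and no comparator or reference value, the trial can describe stability at placement and change over time, but cannot show that the ultra-wide implant enhances primary stability or bone density

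*Combined protocol and SAP*

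**What the plan says.** Under Study Design the protocol states: "The study is a single arm clinical trial". The PICO question that follows asks whether the implant "will enhance primary stability and peri-implant bone density". The PICO elements then give a population, an intervention ("Type of Intervention: immediate placement of ultra wide diameter implant") and outcomes ("Outcomes: wound healing, socket dimensions, crestal bone loss, implant stability and bone density will be the main outcome measures of this study"). There is no comparator line.

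The null hypothesis, at the end of the Introduction, is that using the ultra-wide implant placed immediately after extraction "has no significant effect on implant stability and peri-implant bone density". It does not say relative to what.

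The Aim of the Study is descriptive: to "evaluate both the clinical and radiographical outcome on osteointegration and peri-implant bone density". The Abstract says the same.

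Implant stability is read immediately after surgery and at 6 months (Clinical Evaluation, item 3). Bone density is read from CBCT immediately after surgery and at 6 and 9 months (Radiographic Evaluation). The crown is fitted after 6 months (Prosthetic phase). The Statistical Analysis section names the software only.

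**The concern.** *Enhance* is a comparative verb: the implant must do better than something. The Introduction sets wide implants against conventional ones and immediate placement against delayed placement, but the trial collects data on neither alternative. The intervention joins width and timing, so even a clear change in this arm could not be assigned to either.

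Two things are at stake. On its literal reading, the primary-stability half of the question stays unanswered whatever the data show. And a rise in stability during healing would formally reject a null worded as an effect of using this implant, so an ordinary course of healing could be reported as evidence for the device or for immediate placement.

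**Working it through.** **1. What the sample size is built on.** Inputs from the Summary Statement: ISQ 65.5 (SD 7.6) at baseline and 78.8 (SD 2.8) at 6 months, alpha 5%, power 80%.

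- Difference = 78.8 − 65.5 = 13.3.
- Pooled SD = √((7.6² + 2.8²)/2) = 5.73, so d = 13.3/5.73 = 2.32.
- Two-sided two-sample t-test: 5 per group, power 89%. This reproduces the plan's 5 per group.
- Treated as paired change, SD of change = √(7.6² + 2.8² − 2r × 7.6 × 2.8). The documents give no correlation r, so it is assumed. The number needed is 7 at r = −0.5, 6 at r = 0, 5 at r = 0.2 to 0.5, and 4 at r = 0.7 to 0.9.

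Either way, the effect that sizes the trial is a rise over 6 months in one implant type, not a difference from another implant or from a benchmark. With all 12 patients, paired power for that rise exceeds 99% for r from −0.5 to 0.9. If the planning figures hold, the stability part of the null will almost certainly be rejected, whether or not width or timing contributed anything.

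**2. Is a comparator or reference value given anywhere?**

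- *Cited ISQ figures.* They are introduced as "values at baseline for ultra-wide implants was" 65.5, with 78.8 at 6 months. They come from the same implant type and serve as planning inputs; neither is set as a value to test against. The titles of the two cited trials describe immediate versus later placement, but the plan takes over no delayed-placement figure.
- *Two groups.* These are gender strata within the single arm, not an implant comparison.
- *Materials.* One implant is listed, 7 mm in diameter, so no diameter contrast is planned.
- *Preoperative CBCT.* Its stated purposes are diagnosis and treatment planning; it is not named as a density baseline.
- *Statistical Analysis.* No test, comparator or reference value is named.
- *Participant Safety.* Advantages over the conventional method are mentioned as information for patients; no such data are collected.

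**3. What each outcome can show.**

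- *Primary stability, read literally.* One reading per patient, at placement. Its level can be estimated; enhancement cannot. A higher ISQ at 6 months is later stability.
- *Implant stability.* Two readings, so mean within-patient change to 6 months can be tested. It cannot be separated from healing around an implant of any width.
- *Bone density.* Three readings, the first after placement, so change to 6 and to 9 months can be tested. The same limit applies, and the 9-month change also includes about 3 months after crown placement.

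**4. What precision to expect (illustration only, not evidence of the mismatch).** Half-width of the 95% CI for mean primary ISQ = t × 7.6/√n.

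- n = 12: 2.201 × 7.6/√12 = 4.83.
- n = 10 (5 per stratum retained): 2.262 × 7.6/√10 = 5.44.

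The documents give no planning figures for bone density, so none are computed.

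**The case against.** The strongest reply is that *primary stability* in the PICO question is loose wording. The sentence is grammatically broken, the null and the outcome list both say implant stability, stability is measured twice, and the sample size uses a baseline and a 6-month value. On that reading the question is about pre-post change, which the plan does measure. This stands in part. A reader might infer that the stability question cannot be answered on any reading; the documents do not support that. The looser reading rescues measurability but not attribution: change in one arm still cannot be credited to width or to immediate placement.

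A second reply is that single-arm studies are legitimate and the rest of the plan is non-comparative. This stands. The design is declared openly, the aim is descriptive and can be met, and the null can be tested as within-patient change. The fault lies in a question and a null that claim more than the aim does.

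A third reply is that the harm is conjecture. A reader might infer that the authors intend to report healing as a benefit of the implant. No passage commits them to that, so misreporting remains an inference. Nothing limits the conclusions either, and the null's own wording points that way.

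**Conclusion.** The concern holds in this form: the PICO question and the word *effect* in the null go beyond what a single arm without a comparator or reference value can conclude. The trial can give the level of primary stability at placement and the change in stability and density over follow-up. It cannot show enhancement, and it cannot attribute change to diameter, to immediate placement, or to this implant over conventional ones.

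The conclusion is logical and does not depend on the sample size or on any assumed correlation. The CI half-width of about ±4.8 ISQ with 12 patients assumes the cited SD of 7.6 and only shows what the descriptive question would deliver. The fault is one of wording and inference, not of arithmetic. It should still be corrected, because these sentences define what the trial claims to answer.

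**What to change.** 1. Restate the PICO question: what is the primary stability of these implants at placement, and how do implant stability and peri-implant bone density change over follow-up?
2. Replace the null with separate hypotheses of no mean within-patient change: in ISQ from placement to 6 months; in bone density from immediately after surgery to 6 months; and in bone density from immediately after surgery to 9 months. Report the level at placement and each change as a mean with 95% CI.
3. Add a sentence such as: *Conclusions are limited to level and change over time in this arm; no effect of, or advantage for, implant diameter, immediate over delayed placement, or this implant over conventional implants will be claimed; the 9-month density change also includes loading; results by gender are not a comparison of implants.*
4. Reconcile the 6-month follow-up in the Follow Up policy with the 9 months in the Clinical follow-up phase, the Radiographic Evaluation and the Duration of Study table, since the third hypothesis depends on it.

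The cost is rewording, CIs and one sentence: no new patients or outcomes, no visits beyond those already scheduled, and no change to the gender strata. The downside is a more modest claim.

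If the authors want to keep *enhance*, they need a justified reference value or a comparator, and new sizing. As a guide, at SD 7.6 with a two-sided 5% test and 80% power, 12 patients against a fixed reference detect a difference of about 0.889 × 7.6 = 6.8 ISQ, and 10 patients about 0.996 × 7.6 = 7.6 ISQ.

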## Setting and Location

Participants will be recruited from the Outpatient Clinic of Alexandria University Teaching Hospital and operated in the Oral and Maxillofacial Surgery Department, Faculty of Dentistry, Alexandria University.

## Summary Statement

Sample size was estimated assuming 5% alpha error and 80% study power. Tsallarico et al reported that the mean Implant Stability Quotient (ISQ) values at baseline for ultra-wide implants was  $65.5 \pm 7.6$  and  $78.8 \pm 2.8$  after 6 months of implant placement. The sample will be stratified by gender into two groups. Sample size was calculated to be 5 patients per group, increased to 6 patients to make up for loss to follow up. Total sample size = number per group  $\times$  number of groups =  $6 \times 2 = 12$  patients.

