###### **3- Implant stability.**

- It will be measured by implant stability meter (Osstell™) immediately postoperative and at 6 months.

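### The study question is about primary stability, but the only ISQ contrast in the plan is the rise from placement to 6 months, which cannot answer it

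*Combined protocol and SAP*

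**What the plan says.** - **Question.** The PICO question under Study Design asks whether immediate placement "will enhance primary stability and peri-implant bone density".
- **Null hypothesis.** The Introduction states, more broadly, that the ultra-wide implant "has no significant effect on implant stability and peri-implant bone density".
- **Measurement.** Under Implant stability, ISQ is read "immediately postoperative and at 6 months". The first reading is therefore the plan's measure of primary stability, and the second is stability after healing.
- **Sample size.** The Summary Statement says: "Sample size was estimated assuming 5% alpha error and 80% study power". Its only ISQ inputs are "values at baseline for ultra-wide implants was $65.5 \pm 7.6$ and $78.8 \pm 2.8$ after 6 months of implant placement". It continues: "The sample will be stratified by gender into two groups", and "Sample size was calculated to be 5 patients per group, increased to 6 patients to make up for loss to follow up", which makes 12 in total.
- **Design.** "The study is a single arm clinical trial". No placement ISQ for another implant type and no threshold is given.
- **Analysis.** The Statistical Analysis section names the software and the form of presentation. It names no test or estimate for ISQ.

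**The concern.** Primary stability is a level at one time point. The effect used to size the trial is a change between two time points: 6-month ISQ minus placement ISQ. The quantity asked about enters that change with a negative sign, and no stated analysis estimates it by itself.

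What is at stake is the conclusion. A significant rise could be reported as support for a stability benefit and so taken as the answer to the PICO question. It would show only that ISQ increased during healing, and it would be compatible with good, ordinary or poor stability at insertion.

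**Working it through.** **Inputs (Summary Statement).** Placement ISQ mean 65.5, SD 7.6; 6-month mean 78.8, SD 2.8; alpha 5%; power 80%; 5 per group, raised to 6, 12 in total. Assumed, because the plan does not say: a two-sided test, and a within-patient correlation r between the two readings, taken over its full range where that matters.

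**1. Reproducing the plan's figure.**
- Rise = 78.8 − 65.5 = 13.3.
- Pooled SD = √[(7.6² + 2.8²)/2] = 5.73; standardised effect = 13.3/5.73 = 2.32.
- Two-sample t-test (noncentral t): 5 per group gives power 0.894 and 4 per group gives 0.78, so 5 is the smallest number that reaches 80%. This matches the plan.
- A paired t-test on the same rise needs 6 patients at r = 0 and 5 at r = 0.25 to 0.5.

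The stated 5 therefore follows from the contrast between placement and 6 months. The arithmetic is sound, but it concerns the rise.

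**2. What the rise shows if the trial repeats the cited values.** SD of the change = √(7.6² + 2.8² − 2r × 7.6 × 2.8). Power of a two-sided 5% paired t-test with 12 patients and a mean rise of 13.3:

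| r | SD of change | Power |
|---|---|---|
| −1 (worst case) | 10.40 | 98.0% |
| 0 | 8.10 | 99.9% |
| 0.5 | 6.66 | over 99.9% |

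This is ordinary power for a large, real rise. It carries no information on whether 65.5 is a good level at placement.

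**3. Does better placement stability lower the chance of significance?** Take a mean placement ISQ of 74 or 76 instead of 65.5, with 12 patients and r = 0 to 0.5:

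| Assumption | Power at 74 | Power at 76 |
|---|---|---|
| 6-month mean stays at 78.8, placement SD 7.6 | 47–62% | 20–27% |
| 6-month mean rises by half the shift, placement SD 7.6 | 94–99% | 88–97% |
| 6-month mean stays at 78.8, placement SD 2.8 | 97% or more | 61–88% |

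In the second row the mean rise is 13.3 − 8.5/2 = 9.05 at 74 and 13.3 − 10.5/2 = 8.05 at 76. If the 6-month mean rose by the full shift, the rise would stay at 13.3 and power would not change. The direction and size of the effect thus depend on assumptions that the documents do not supply. In none of these cases does the test of the rise detect the better placement level.

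**4. Precision for the quantity that is asked about.** The half-width of the 95% confidence interval for mean placement ISQ is t × SD/√n, with SD 7.6:
- n = 12: 2.201 × 7.6/√12 = 4.8 ISQ.
- n = 10: 2.262 × 7.6/√10 = 5.4 ISQ.

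**The case against.** Four points can be made for the plan.

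1. *No test of the rise is written down.* This stands. The analysis section names only software, and the sample is split by gender, so a comparison of men with women is possible. That comparison has no stated effect, however, and would not answer the PICO question. The rise is the likely contrast, but only by inference. Nor does the plan say that the rise will be read as evidence on primary stability.
2. *Only the PICO sentence says primary.* This also stands. The null hypothesis and the outcome list speak of implant stability in general, and the aim speaks of osseointegration. A change over 6 months is a reasonable measure of gain during healing. The mismatch is with the PICO question.
3. *A reader might infer that the test necessarily points the wrong way*, with success on primary stability making a finding of no effect more likely. The documents do not support that as a general statement. It needs a 6-month level that does not rise as much as the placement level. The small 6-month SD (2.8 against 7.6) fits a plateau but does not prove one. Even with the 6-month mean and both SDs held fixed, power at n = 12 stays above 80% until mean placement ISQ passes about 72 to 73 (r = 0 to 0.5).
4. *A reader might also treat the near-certain rejection at 65.5 as a false-positive rate for a trial with no gain in primary stability.* That is unsupported too. The cited 65.5 is itself an ultra-wide value, so it may already contain any advantage, and the rise being detected is real.

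A comparator measured at placement would allow a direct contrast of primary stability, so this point is linked to the single-arm design. Adding a comparator would still require naming placement ISQ as the quantity compared.

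**Conclusion.** The concern holds as a mismatch between question and contrast. The PICO question is about ISQ at placement. The only contrast in the plan, and the one that reproduces 5 per group, is the rise to 6 months. Whichever way the 6-month level moves, a rise cannot show whether primary stability was good. With the cited means and SDs and a two-sided paired test in 12 patients, it would be significant at least 98% of the time at any correlation. That the rise is the intended test is inferred. That its significance would fall as placement stability improves is conditional and not established. The sample-size arithmetic is not at fault. The plan should be corrected before analysis.

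**What to change.** In the Introduction (null hypothesis), Study Design (PICO question), Summary Statement and Statistical Analysis:

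1. Define primary stability as the immediate postoperative ISQ. Report its mean and 95% confidence interval in all implants placed, and state the expected half-width (about 4.8 ISQ with 12 patients, 5.4 with 10, if the SD is 7.6).
2. Analyse the change from placement to 6 months with a paired test, label it gain in stability during healing, and always show it with both levels.
3. State that the size and p-value of the rise are not evidence about primary stability, and that the sample size concerns the rise only.
4. State that 65.5 ± 7.6 is itself an ultra-wide figure, so setting the trial mean beside it is descriptive. State that without a comparator the trial cannot conclude that primary stability was enhanced, and reword the PICO question to match.

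Both readings are already planned, so no extra patients or measurements are needed. The cost is rewording, and a near-certain significant p-value can no longer be presented as the answer on primary stability.
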